12.0 STATISTICAL CONSIDERATIONS

12.1 STUDY DESIGN/STUDY ENDPOINTS

The study is an open-label, non-randomized single-arm, single institution phase Ib/II therapeutic clinical trial. The study population will be patients with advanced hepatocellular carcinoma.

The phase Ib component of the study will consist of a traditional 3+3 dose escalation rule with 3 or 6 patients in each cohort, the process for dose escalation is outline in section 6.4.

The primary endpoint of the phase II component will be progression free survival (PFS) of

HCC patients. PFS is defined to be the time from initiation of treatment to progression or death without evidence of progression. For cases without documentation of progression, follow-up will be censored at the date of last disease assessment without progression, unless death occurs within 4 months following the date of last progression-free, in which case death will be counted as an event. The historical median PFS for TACE alone is 8-10 months. Our institutional median PFS following the TACE protocol outlined is 8.0 months. This study will target a hazard ratio of 0.69 with an 80% power and a one-sided significance level of 10%. Assuming a 24-month accrual and an 18-month follow-up period the study requires 38 patients initiating LEE011 treatment with the median PFS for TACE alone is 8 months, and 40 patients with the median PFS for TACE alone is 10 months. PFS will be estimated using the Kaplan-Meier method, and Greenwood's formula will be used to calculate the standard error of the corresponding Kaplan-Meier estimate and 95% confidence interval. Survival curves will be estimated using Kaplan-Meier methodology. Forty total patients will be enrolled in the phase II aspect of the trial. This includes only patients who undergo chemoembolization and initiate LEE011 therapy.

Secondary endpoints of efficacy are to evaluate OS. The statistical methods used for the analysis of PFS will be used for the analysis of OS.

Other secondary objectives will include description of toxicity of the therapy regimen. These data will be analyzed separately. The safety analyses will be performed on all patients who receive any dose of therapy. Adverse events will be described using the NCI CTCAE v 4.03 criteria (ctep.cancer.gov/forms/CTCAEv4.pdf). Frequency and severity of adverse events according to the NCI CTCAE v# body system and severity criteria will be described. In addition, frequency of Grade 3 or 4 adverse events will be described separately. Causality will also be noted. Adverse events will be recorded for up to 1 year following discontinuation from study. Response rate and toxicity rate will be estimated using an exact binomial method along with the 95% confidence interval.

Laboratory assessments will also be described according to the NCI CTCAE v. 4.03 criteria, with separate descriptions for Grade 3 or 4 laboratory abnormalities. Clinically significant laboratory abnormalities will be described as well. Serious adverse events will be summarized, including a causality assessment.

The number of treatment cycles and doses administered will be summarized using descriptive statistics. Treatment delays will be summarized using counts and percentages.

Patients' disposition will be summarized in the following manner:

- The number and percentage of patients selected, included, completed, withdrawn and lost to follow-up will be summarized using descriptive statistics;
- Major protocol deviations will be summarized;
- The reason for withdrawal (adverse events, lack of efficacy, major protocol deviation, non-medical reason, recovery or remission) will be summarized.

For pathology-, laboratory- and imaging-correlative studies, Cox regression analysis will be

conducted to investigate the association between PFS and parameters from correlative studies.

Approximately 175-200 patients with HCC are seen annually at UT Southwestern Medical Center with 80-90 chemoembolizations performed. We anticipate no potential problems meeting the accrual deadlines with the proposed trial. In addition, there are no competing trials either nationally or at UT Southwestern for this patient population that would potential limit accrual.

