and reported a significant result in favor of chemoembolization. One and 2 year survival probabilities were 82% and 63% for chemoembolization; 63% and 27% for BSC, $p=0.009$. (5) In a single institution study from Hong Kong, Lo and colleagues randomized 80 patients to either BSC or cisplatin based chemoembolization. Survival for the chemoembolization arm (1 year, 57%, 3 years, 26%) was superior to the BSC arm (1 year, 32%; 3 years, 3%, $p=0.002$). A subsequent meta-analysis of randomized trials in HCC conducted between 1978 and 2002 with a combined total of 545 patients reported a significant improvement of 2 year survival in favor of chemoembolization, OR 0.42; 95% CI, 0.2-0.88. Multiple studies have demonstrated median progression free survival times ranging from 8-10 months. (6) Our institutional historical controls for chemoembolization demonstrate an 8.0 month median PFS. Chemoembolization has become the accepted standard of treatment option for local advanced HCC with no curative options. The NCCN, the American Association for the Study of Liver Diseases, and the Barcelona Clinic Liver Cancer Group, all recommend chemoembolization for the treatment of unresectable HCC. (7)

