2.0 STUDY OBJECTIVES

2.1 PRIMARY OBJECTIVE

- 2.1.1 To determine the maximum tolerated dose (MTD) of LEE011 in patients with locally advanced HCC treated with chemoembolization. (Phase Ib)
- 2.1.2 To determine the progression free survival (PFS) of combination LEE011 and chemoembolization in patients with locally advanced HCC. PFS will be calculated from the date of enrollment on the study to appearance of new metastatic lesions or objective tumor progression using RECIST version 1.1 guidelines and be compared with historical controls. (Phase II)

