3.1 ENDPOINTS

Phase Ib:

The primary endpoint of the phase Ib trial will be determination of the maximum tolerated dose of LEE011 administered following chemoembolization (section 6.6).

Phase II:

The primary endpoint of the phase II trial will be progression free survival (PFS) of HCC patients.

Statistics and sample size justification:

PFS is defined to be the time from initiation of treatment to progression or death without evidence of progression. For cases without documentation of progression, follow-up will be censored at the date of last disease assessment without progression, unless death occurs within 4 months following the date of last progression-free, in which case death will be counted as an event. The historical median PFS for TACE alone is 8-10 months. Our institutional median PFS for TACE based on similar chemoembolization procedures as outlined below is 8.0 months. This study will target a hazard ratio of 1.45 with an 80% power and a one-sided significance level of 10%. Assuming a 24-month accrual and an 18-month follow-up period the study requires 40 patients initiating LEE011 treatment with the median PFS for TACE alone is 8 months. PFS will be estimated using the Kaplan-Meier method, and Greenwood's formula will be used to calculate the standard error of the corresponding Kaplan-Meier estimate and 95% confidence interval. Survival curves will be estimated using Kaplan-Meier methodology.

Secondary endpoints of efficacy are to evaluate OS. The same statistical methods used for the analysis of PFS will be used for the analysis of OS.

Other secondary objectives will include description of toxicity of the therapy regimen. These data will be analyzed separately. The safety analyses will be performed on all patients who receive any dose of therapy. Adverse events will be described using the NCI CTCAE v. 4.03 criteria (ctep.cancer.gov/forms/CTCAEv4.pdf). Frequency and severity of adverse events according to the NCI CTCAE v. 4.03 body system and severity criteria will be described. In addition, frequency of Grade 3 or 4 adverse events will be described separately. Causality will also be noted. Adverse events will be recorded for up to 30 days following discontinuation of LEE011 or followed until resolution, whichever comes first. Response rate and toxicity rate will be estimated

using an exact binomial method along with the 95% confidence interval.

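### The phase II PFS comparison is powered at 80%, one-sided 10%, but the only PFS analysis written is Kaplan-Meier with a 95% interval; no test, success rule or tested null is stated

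*Combined protocol and SAP*

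**What the plan says.** Section 2.1 makes PFS the phase II primary objective, with "objective tumor progression using RECIST version 1.1 guidelines and be compared with historical controls". Section 12.1 gives the design values: "This study will target a hazard ratio of 0.69 with an 80% power and a one-sided significance level of 10" per cent, with 24 months of accrual and 18 months of follow-up. Section 3.1 gives the same power and level, but writes the hazard ratio as 1.45.

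On analysis, section 12.1 says "PFS will be estimated using the Kaplan-Meier method", and that Greenwood's "formula will be used to calculate the standard error of the corresponding Kaplan-Meier estimate and 95% confidence interval". Section 3.1 says the same. Cox regression appears in both sections for correlative parameters only. OS borrows the PFS methods. Section 9.4 plans no interim analysis.

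On the reference value, both sections give a historical range of 8-10 months. Section 1.2 states "Our institutional historical controls for chemoembolization demonstrate an 8.0 month median PFS", section 3.1 states "Our institutional median PFS for TACE based on similar chemoembolization procedures as outlined below is 8.0 months", and section 12.1 repeats 8.0. For the sample size, section 3.1 says "the study requires 40 patients initiating LEE011 treatment with the median PFS for TACE alone is 8 months", while section 12.1 says "the study requires 38 patients initiating LEE011 treatment with the median PFS for TACE alone is 8 months, and 40 patients" at 10 months. Forty are to be enrolled.

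**The concern.** A power and a one-sided level have meaning only for a test with a stated null and boundary. Here they are attached to an estimation plan. A two-sided 95% interval corresponds to a one-sided 2.5% criterion, not 10%, so anyone who reads the planned interval as the decision rule applies a stricter standard than the trial was sized for.

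The reference value is also left to inference. Section 12.1, the dedicated statistics section, carries 8 and 10 months side by side. In an open-label, single-institution trial, the choice of test, level and null could then be made with the data in view, and it would decide whether the primary endpoint is called positive.

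**Working it through.** **Inputs.** Hazard ratio 0.69, power 80%, one-sided 10%, accrual 24 months, follow-up 18 months, N = 40, reference medians 8 and 10 months (sections 3.1 and 12.1). Assumed, because the plan does not state them: exponential PFS, uniform accrual, no dropout. Normal quantiles: 1.2816 (one-sided 10%), 0.8416 (80% power), 1.96 (one-sided 2.5%). Target medians: 8/0.69 = 11.6 and 10/0.69 = 14.5 months.

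**1. Reproducing the plan's N**
- Events: (1.2816 + 0.8416)² / ln(0.69)² = 32.7.
- Event probability: p = 1 − [exp(−18λ) − exp(−42λ)]/(24λ), with λ = ln 2/median. This gives 0.912 at 8 months, 0.819 at 11.6, 0.860 at 10 and 0.749 at 14.5.
- One-sample exponential log-hazard test: N = [(1.2816/√p0 + 0.8416/√p1)/ln(0.69)]². Null 8: 37.5. Null 10: 40.3. These sit close to section 12.1's 38 and 40.
- Dividing by the target event probability alone: 32.7/0.819 = 40.0 at null 8, which matches section 3.1.
- A two-arm comparison would need 131 events (Schoenfeld), so the plan's N implies a one-sample test against a fixed reference.
- 1/0.69 = 1.45, so the two hazard ratios describe the same effect in opposite directions.

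**2. Power at N = 40, null 8, true median 11.6.** Expected events: 40 × 0.819 = 32.8. The standardised effect is √32.8 × 0.371 = 2.12.
- One-sided 10%: Φ(2.12 − 1.28) = 80%.
- One-sided 2.5% (95% interval): Φ(2.12 − 1.96) = about 56-57%.
- Simulation of the one-sample log-rank test, z = (E − O)/√E, 40,000 trials: about 80% and about 56%.

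**3. Null 8 against null 10, N = 40, one-sided 10%**
- True median 11.6, null 10: √32.8 × ln(11.6/10) = 0.85, so Φ(0.85 − 1.28) = 33%. The gap from 80% is about 47 points. In simulation, about 48% of trials pass against 8 and fail against 10.
- True median 14.5, null 10: 40 × 0.749 = 30 events, so Φ(√29.9 × 0.371 − 1.28) = 77%. The simulated log-rank gives about 78%.

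**4. Cost of the lenient null.** If TACE alone truly gives 9 or 10 months and the drug adds nothing, the simulated log-rank against 8 passes about 27% or 50% of the time. The exponential formula gives 28% and 51%.

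**5. Time origin.** Section 2.1 starts PFS at enrolment; sections 3.1 and 12.1 start it at treatment initiation. Section 12.1 counts only patients who start LEE011. By section 6.12 that is at least 7 days after chemoembolization, with removal if starting criteria are not met within 28 days. Suppose the clock starts at chemoembolization and the historical series had no such lead-in. A common event-free lead-in of 7, 14 or 28 days then gives a simulated type I error of about 11%, 13% or 19%, against about 9% with none. This is conditional: the documents do not give the origin of the historical 8.0 months.

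**The case against.** The strongest reply is that the design can be recovered. Section 3.1 sizes on 8 months alone, and the institutional 8.0 is stated three times. Hazard ratio, power, level, sidedness, accrual, follow-up and N are all written. The second figure in section 12.1 can be read as a check that 40 patients also cover 10 months. Much of this stands: 8.0 months is the natural null, and it would be too strong to say that the null cannot be determined. What does not follow is the test, the boundary or the decision rule, since the only interval written is at another level. Section 12.1 still does not say which of its two values is tested.

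It can also be said that a single-arm phase II trial may simply estimate. This one commits to a comparison in section 2.1 and sizes itself on error rates.

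A reader might infer more than the documents support:
- **That the sample size is wrong.** It is not. Both 38 and 40 reproduce from the plan's inputs under standard conventions, and the 38/40 and 0.69/1.45 differences do not change enrolment.
- **That a band of observed medians marks the disputed zone.** The two boundaries convert to medians only for an exponential estimate at a fixed event count; the plan reports a Kaplan-Meier median.
- **That only one test is acceptable.** The exponential log-hazard test reproduces 38 and 40 well, so the sponsor should be free to name the test behind its own N.

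**Conclusion.** The point holds as a gap in the primary analysis, not in the sample size. The stated one-sided 10% is tied to no test, no boundary and no designated null, and the one interval the plan specifies corresponds to a stricter level. At the plan's target effect, reading that level as the rule lowers power from about 80% to about 56% (null 8 months). Moving the null from 8 to 10 months changes the verdict in about 48% of trials. These figures rest on exponential PFS, uniform accrual, 40 patients, no dropout and continuously observed progression. The absence of a rule does not depend on those assumptions. It should be settled before the PFS analysis, because a rule chosen after the data are seen cannot carry the stated error rate.

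**What to change.** Before analysis, put one identical statement in sections 3.1 and 12.1 that gives:
- **Null:** the institutional 8.0-month median, or another value the sponsor justifies.
- **Test:** a one-sample test against that fixed reference at one-sided 0.10. Examples are the one-sample log-rank with success if z = (E − O)/√E > 1.2816, or the exponential log-hazard test.
- **Design values:** hazard ratio 0.69 (median 11.6 months), N = 40, about 33 events, power about 80%. If 10 months is chosen as the null, restate power as about 78% with about 30 events.
- **Time origin:** one start date for PFS, reconciling section 2.1 with sections 3.1 and 12.1, and matching the origin behind the historical 8.0 months.

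Report the matching two-sided 80% interval; for the log-rank, log(O/E) ± 1.2816/√O. Keep Kaplan-Meier with its 95% interval as description, and report the 10-month comparison as a sensitivity analysis. State one N at 8 months and one hazard ratio direction.

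The cost is wording in sections 3.1 and 12.1, alignment of section 2.1, and one more reported interval, with no added patients at a null of 8.0. The downside is that 8.0 is the lenient end of the plan's own 8-10 month range, so the sponsor should defend it openly and limit any claim to that benchmark.

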5.1 INCLUSION CRITERIA

- 5.1.1 Histologically confirmed diagnosis of hepatocellular carcinoma (mixed HCC/cholangiocarcinoma is allowed).
- 5.1.2 **RB positivity as defined by RB expression (score of 0.5 or 1) with concurrent p16in4a loss (score of 0-2);**
- 5.1.3 Patients must have HCC limited to the liver. There must be no definitive

clinical or radiographic evidence of extrahepatic HCC. Portal lymphadenopathy is permitted as lymphadenopathy is commonly associated with cirrhosis unrelated to malignancy;

- 5.1.4 Absence of occlusive main portal vein thrombus, branch venous thrombus is allowed;
- 5.1.5 Patients with locally advanced HCC not eligible for curative therapies;
- 5.1.6 Age \geq 18 years;
- 5.1.7 Child-Pugh Score A or B7;
- 5.1.8 ECOG Performance score of 0-2;
- 5.1.9 Anticipated life expectancy greater than 6 months;
- 5.1.10 Following baseline laboratory values should be met:
 - 5.1.10.1** Total bilirubin \leq 2.0 x ULN or direct bilirubin \leq 1.5 x ULN in patients with well-documented Gilbert's Syndrome;
 - 5.1.10.2** INR \leq 1.7;
 - 5.1.10.3** Hgb \geq 9.0 g/dl;
 - 5.1.10.4** Alkaline Phosphatase, AST, ALT $<$ 5 times ULN;
 - 5.1.10.5** Platelet count \geq 75,000/mm³;
 - 5.1.10.6** Serum creatinine \leq 1.5 mg/dL or creatinine clearance \geq 50 mL/min;
 - 5.1.10.7** Absolute neutrophil \geq 1,500 cells/mm³;
 - 5.1.10.8** Potassium, total calcium (corrected for serum albumin), magnesium, and phosphorus within normal limits for the institution or corrected to within normal limits with supplements;
- 5.1.11 Women of childbearing potential must have a negative pregnancy test;
- 5.1.12 Prior therapy is allowed provided the following are met: at least 4 weeks since prior locoregional therapy including surgical resection, radiotherapy, or

ablation. Provided target lesion has increased in size by 25% or more or the target lesion was not treated with locoregional therapy;

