6.6 DOSE LIMITING TOXICITIES-PHASE IB COMPONENT

The phase Ib component of the study will consist of 3+3 dose escalation rule with the dose of LEE011 escalating up to 600mg daily to determine the maximum tolerated dose (MTD) that will be used during the phase II component. The dose levels for the phase Ib aspect will be 200 mg, 400 mg, or 600 mg daily.

Only the first cycle of therapy (one cycle equals to one month) will be used to determine dose limiting toxicity (DLT). However, if two total grade 5 adverse events or 2 Grade 4 adverse events (lasting ≥ 7 days); occur at any time while the patient is still receiving study treatment that are either: definitely, probably, or possibly related to either LEE011 or TACE the study will be terminated to enrollment.

Only patients started on the first dose of LEE011 will be included in the evaluation of DLT. If a patient has a DLT that patient will not receive further LEE011. Patients following initial chemoembolization who never receive LEE011 will not be included in the MTD analysis and will be replaced. The patients will be followed for thirty days following the initial chemoembolization for safety assessment. Patients will be enrolled into the next highest drug cohort only after 3 or 6 patients have completed the first cycle of therapy. Once the MTD is determined, patients at the MTD dose will continue with LEE011 and represent the first three patients accrued to the phase II aspect.

Due to observed (TACE related, non DLT) toxicity on cohort 1 specific criteria for cohort 1 has been developed after discussion with the FDA. Cohort 1 has been expanded to 6 patients. Decision for dose escalation will be made using the following criteria:

- No or one DLT: the next three patients will be assigned to next higher dose level (400 mg of LEE011).
- At least two toxicities: the MTD is exceeded and the phase I component of the trial will be stopped with no continuation into the phase II component.

For Cohort 2 and 3 the following traditional 3+3 dose escalation rules will be used:

- If a dose limiting toxicity (DLT) is observed in 1 out of 3 patients at a given dose level, up to 3 additional patients will be enrolled and treated at that dose level.
- If 2 out of 3-6 patients at that dose level have DLTs, the dose will be decreased to the previous dose level, and up to 3 additional patients will be enrolled at that dose level for a total of 6 patients.

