 - Physical examination
 - Comprehensive metabolic panel
 - Complete blood count without differential
 - Prothrombin time/INR

At this time the decision will be made to initiate LEE011 treatment.

LEE011 ADMINISTRATION WITH CHEMOEMBOLIZATION

Subjects are to be evaluated from toxicity with:

- Physical Examination (PE)
- Comprehensive Metabolic Panel (CMP)
- CBC
- ECG's

LEE011 will be initiated at the earliest of 7 days following embolization chemoembolization provided the following criteria are met:

- Serum bilirubin elevation $< 2.0 \times \text{ULN}$. If serum bilirubin $\geq 2.0 \times \text{ULN}$ then subjects will be assessed weekly and LEE011 will be initiated once bilirubin $< 2.0 \times \text{ULN}$.
- Resolution of Grade < 3 non-hematologic toxicity (other than bilirubin criteria above). If non-hematologic toxicity \geq Grade 3 then subjects will be assessed weekly and LEE011 will be initiated once $<$ Grade 2;
- Hematological toxicity of \leq Grade 2. If hematologic toxicity \geq Grade 3 then subjects will be assessed weekly and LEE011 will be initiated once \leq Grade 2.

If baseline AST, ALT and alkaline phosphate are elevated post chemoembolization decrease to baseline grade is necessary to continue/initiate LEE011;

- ECOG performance status ≤ 2 ;
- Serum AST, ALT, and/or Alkaline Phosphate $< 5 \times \text{ULN}$.

If criteria is not met, subjects will be reevaluated in 5-7 day intervals. If study subjects are unable to meet the above LEE011 starting criteria following initial chemoembolization treatment within 28 days after treatment, they will be removed from the study.

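### Phase II PFS has conflicting time origins and counts only patients who start LEE011 after TACE, while the 8.0-month TACE benchmark has no stated selection or origin

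*Combined protocol and SAP*

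**What the plan says.** **Who is counted.** Section 12.1 sizes phase II on patients who begin LEE011 and says of the forty: "This includes only patients who undergo chemoembolization and initiate LEE011 therapy".

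**How patients reach that set.** Under LEE011 Administration with Chemoembolization (section 6.12), "LEE011 will be initiated at the earliest of 7 days following embolization chemoembolization", subject to bilirubin, toxicity-grade, liver-enzyme and ECOG conditions. Some repeat entry limits, such as "ECOG Performance score of 0-2" in section 5.1. Others are new, for example: "If baseline AST, ALT and alkaline phosphate are elevated post chemoembolization decrease to baseline grade is necessary to continue/initiate LEE011". On those who do not qualify, the text is: "unable to meet the above LEE011 starting criteria following initial chemoembolization treatment within 28 days after treatment, they will be removed from the study".

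**When the clock starts.** Section 2.1.2 counts PFS from enrollment. Sections 3.1, 8.1.5 and 12.1 count it from initiation or start of treatment.

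**What it is compared with.** Section 1.2: "Our institutional historical controls for chemoembolization demonstrate an 8.0 month median PFS". Section 3.1: "Our institutional median PFS for TACE based on similar chemoembolization procedures as outlined below is 8.0 months". Section 12.1 repeats the figure, again by reference to the TACE protocol. No section gives the benchmark's patient selection, time origin or scan interval.

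**What happened in phase Ib.** Section 6.6: "Due to observed (TACE related, non DLT) toxicity on cohort 1 specific criteria for cohort 1 has been developed". The same section provides for replacing phase Ib patients who never receive LEE011. It does not say whether any patient failed to start.

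**The concern.** The only efficacy comparison is with historical TACE, so the trial patients and the benchmark need the same entry condition and the same time zero. Neither is secured.

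Patients who recover slowly after TACE, or do not recover, drop out before they count. If they have a worse outlook and the benchmark includes such patients, the starters look better even if LEE011 does nothing. If instead PFS is timed from LEE011 start and the benchmark from TACE, the trial gives away up to four weeks per patient and loses power. The reader cannot tell which of these applies, so both a positive and a negative result would be hard to interpret.

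**Working it through.** **1. The plan's own sample size reproduces.** Inputs from section 12.1: HR 0.69, one-sided 10%, 80% power, 24 months' accrual plus 18 months' follow-up, null median 8 months. No test is named. I assumed a one-sample log-rank test against an exponential curve.

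- Hazard under the target: λ₁ = 0.69 × ln 2 / 8 = 0.0598 per month.
- Event probability: v₁ = 1 − (e^(−18λ₁) − e^(−42λ₁)) / (24λ₁) = 0.819. Expected events per patient under the null curve: v₀ = 0.819 / 0.69 = 1.187.
- n = (1.2816·√((v₀+v₁)/2) + 0.8416·sd₁)² / (v₀−v₁)², where sd₁ = 1.169 is the SD of observed minus expected. This gives 2.267² / 0.368² = 38.0 (stated: 38).
- With a 10-month null, n = 40.5 (stated: 40). Section 3.1's 40 at 8 months follows from 32.7 events / 0.819 = 40.0.
- Simulated at n = 40 with an 8-month null: type I error 0.09, power 0.80.

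The arithmetic is sound. The problem is comparability.

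**2. The time origin, text against text.**

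| Place | What it implies |
|---|---|
| 2.1.2 | Enrollment |
| 3.1, 8.1.5, 12.1 | Initiation or start of treatment |
| 6.2 | Study treatment is TACE plus LEE011, so first TACE |
| 8.0 | Scans timed from the initial TACE |
| Table 7.1, note 2 | First treatment day is Cycle 1 Day 1, in the LEE011 columns |

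**3. Follow-up of non-starters, text against text.** Section 6.12 removes them. Section 6.5 follows for survival those who come off therapy, whatever the cause. Table 7.1 note 12 and section 7.5.1 follow all patients. But 7.5.1 starts at the Safety Follow-Up visit, which Table 7.1 and section 7.4.2 time from the last LEE011 dose. A non-starter has no such date.

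**4. Selection (illustration).** The documents give no non-starter share f or prognosis, so both are assumed. Suppose the whole TACE cohort has a median of 8 months. Then f·S_non(8) + (1−f)·S_start(8) = 0.5. With f = 10% and a non-starter median of 4 months, S_non(8) = 0.25 and S_start(8) = (0.5 − 0.025)/0.9 = 0.528. The starters' median is 8 × ln 2 / (−ln 0.528) = 8.68 months with no drug effect. False-positive rates at n = 40, nominal 10%:

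| Assumed share, median | Starters' median (months) | Against whole-cohort curve | Against 8-month exponential |
|---|---|---|---|
| 5%, 4 months | 8.31 | 11–12% | 13% |
| 10%, 6 months | 8.27 | 12% | 13% |
| 10%, 4 months | 8.68 | 16% | 20% |
| 15%, 4 months | 9.11 | 21–22% | 29% |
| 10%, 2 months | 9.24 | 20% | 32% |
| 15%, 2 months | 10.09 | 29–30% | 52% |

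Part of the last column is curve misfit: with all non-starters included, the rate is still 10–23%.

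**5. Clock mismatch (illustration).** The target median is 8 / 0.69 = 11.6 months, a gain of 3.6. A shift of 7 to 28 days is 0.23 to 0.92 month, or 6% to 26% of that gain. If every PFS time is shortened by the delay and tested against an 8-month exponential, power falls from 80% to 77%, 74% and 67% at 7, 14 and 28 days, and type I error to 7%, 5–6% and 4%. A model with 8-weekly then 12-weekly scans, and a benchmark scanned on the same grid, gives power of 64–73%. With trial scans against a smooth 8-month exponential it is 79% at 7 days and 70–71% at 28. The loss is real in these models, but its size depends on the delay and the benchmark's scan schedule.

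**The case against.** **The starter set is declared.** Section 12.1 states it and sizes the trial on it, and such sets are common in phase II. This stands, and starters can remain primary. The difficulty is that nothing says the benchmark was conditioned in the same way.

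**Non-starters are not ignored.** A reader might infer that no planned analysis includes them. The documents do not support that. Sections 3.1 and 12.1 plan a disposition summary with reasons for withdrawal, and safety covers all who receive any therapy, which under section 6.2 arguably includes TACE alone (section 8.2 speaks of study drug). What is missing is an efficacy analysis.

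**The text leans towards first TACE.** Sections 6.2 and 8.0 point that way, and note 2 of Table 7.1 is a scheduling footnote. This narrows the second ambiguity, but the conflict between enrollment and treatment start remains.

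**The error rates are assumptions.** This stands. The rows with a 2-month median are strained: the start criteria concern toxicity, liver function and performance status, the first scan is at 8 weeks, and nothing suggests half of non-starters would progress by about then. A reader might also infer from the cohort 1 toxicity that patients failed to start. The text does not say so.

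**The remedy stays imperfect.** The institutional curve is not shown to be RB-selected. That stands as a limitation to report.

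**Conclusion.** The conflicting time origin of the primary endpoint is wrong as written. The sensitivity analysis including non-starters is a cheap improvement. The undescribed benchmark is missing detail that makes both matter.

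A reader might conclude that the trial is biased in favour of LEE011. The documents do not support a direction: selection may favour the combination, a LEE011-start clock against a TACE-origin benchmark works against it, and the two can partly cancel. If the start criteria are not prognostic and the clocks match, there is no bias.

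The size is illustrative: about 16% to 20% false positives instead of a nominal 10% if 10% of patients do not start and their median PFS is 4 months, and power below 80% by a model-dependent amount if the clocks differ. These figures rest on an assumed non-starter share, prognosis, test and benchmark scan schedule. The stated sample size is not in question.

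**What to change.** 1. **One time origin.** State it in sections 2.1.2, 3.1, 8.1.5 and 12.1, and apply it to the benchmark. If it is first TACE, count the starters' observed and expected events only from LEE011 start (delayed entry). If it is LEE011 start, restart the benchmark at the same post-TACE landmark.
2. **Non-starters.** Keep LEE011 starters as the primary set. Reconcile the removal sentence in section 6.12 with section 6.5, Table 7.1 notes 5, 11 and 12, and sections 7.4.3 and 7.5.1, so that RB-eligible, TACE-treated non-starters stay in PFS and OS follow-up. RB-negative patients remain screen failures (Table 7.1, note 7). Pre-specify one sensitivity analysis of PFS from first TACE in all RB-eligible TACE-treated patients against the institutional TACE curve.
3. **Benchmark (supporting).** Report its population, origin and scan interval. Unless records allow it to be restricted, state as a limitation that it is not known to be selected on RB status or on the start criteria.

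The cost is protocol wording, a query of institutional records that may be incomplete, and a possibly less favourable comparison. Extra follow-up covers about 2 to 7 patients if 5–15% do not start (40 × 0.05/0.95 = 2.1; 40 × 0.15/0.85 = 7.1). In the illustration the sensitivity analysis has power of 74–79%, which is why it is secondary. The primary sample size does not change.
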